Study intervention	
 Each cluster will be randomized to one of the two antithrombotic regimens: prophylactic-dose or intermediate dose as described above. The choice of agents will be dependent upon the renal function (at the time of enrollment and every subsequent day). At the onset of study enrollment, clusters including patients admitted within the past 5 days will be randomized. Patients who meet eligibility by screening team will be enrolled. Patient is considered enrolled after a co-investigator has confirmed all inclusion/exclusion criteria have been met. Assessment of appropriateness of anticoagulation dose will occur daily based on the renal function, progressive thrombocytopenia or anemia, or development of another indication for anticoagulation such as new-onset atrial fibrillation, Patients' treatment course will be followed from randomization to hospital discharge or 30 days, whichever happens earlier. Patients will continue with randomization therapy until discharged from the ICU, except in the setting of an adverse event attributed to anticoagulation, developing an event requiring therapeutic anticoagulation, or change in code status to comfort measures. Patients transferred between participating ICUs will remain in the treatment arm assigned at initial randomization. Recommendation will be to continue study treatment if patient transferred to ICUs not participating in the present trial. If the study treatment is changed by the primary treating team in the second ICU, then patient will be evaluated by intention to treat principle. 
Intervention arm: intermediate-dose anticoagulation
 
 If stable eGFR ≥ 30 mL/min: enoxaparin 1mg/kg SC daily¹ If eGFR <30 mL/min or acute kidney injury (as defined below) or CRRT: Unfractionated heparin infusion at 10 units/kg/hour (minimum 500 units/hour if CRRT) with goal anti-Xa 0.1-0.3 U/mL² 
Control arm: Prophylactic dose anticoagulation (per CUIMC Guidelines):
 
 If eGFR ≥ 30 mL/min (stable kidney function): 
 BMI < 40 kg/m²: Enoxaparin 40 mg SC daily BMI 40 – 50 kg/m²: Enoxaparin 40 mg SC q12h BMI > 50 kg/m²: Enoxaparin 60 mg SC q12h If eGFR < 30 mL/min or acute kidney injury: • If eGFR < 30 mL/min or acute kidney injury:

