Potential benefits of intermediate-dose vs. prophylactic dose anticoagulation	
 • Potential for reduced risk of thrombotic complications (including VTE, MI, stroke, and line thrombosis) • Potential for improving the recovery from need from mechanical ventilation. • Potential for reducing the risk of DIC. • Potential for reducing the risk of renal failure. • Potential for reducing mortality as a result of reducing the above components.
Potential risks of intermediate-dose vs. prophylactic dose anticoagulation	
 • Increased risk of bleeding, including major bleeding • Heparin induced thrombocytopenia

VIII. Study Design and Analysis Plan (include timing and primary and secondary endpoint analysis)

In order to assess event rates and appropriately adjust study measures as part of adaptive trial design, a blinded interim analysis at the combined event rate of both study arms will be performed. Once the trial is completed, analysis will be performed by intention to treat.

General Design

This is a cluster randomized-controlled clinical selection trial of interventions for anticoagulation for COVID-19 patients in the ICU. ICU subunits will be randomly assigned to give patients intermediate (higher) dose or prophylactic (lower) dose of anticoagulation. The primary goal of the trial is to select the best intervention with a high probability of *correct* selection if one intervention is truly superior by a pre-specified effect size. Up to 100 patients (with expected sample sizes between 69-75 patients for the most likely scenarios) will be enrolled in the study, using a novel sequential design. Each time an outcome is observed for a patient, those outcomes are added to a running tally of successes for each intervention. There is a pre-specified criterion in terms of the success tallies for selecting arm as evidence of apparent superiority accumulates. With this sequential procedure, the preferred intervention can be selected during the ongoing enrollment as soon as the pre-specified selection criteria are met, and further enrollment will cease. To ensure that there will be some unbiased estimates of the proportion of patients with a good outcome available for each intervention arm, the selection criteria will not be applied until 60 patients have been observed. This novel approach based on the Levin-Robbins-Leu family of sequential selection procedures [18-23].

Study Implementation

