The identification of a preferred treatment will be done using an innovative sequential selection procedure, which will substantially reduce the number of patients in comparison to a hypothesis test procedure. The data will be examined each time a pair of patients completes follow-up after 60 patients have been observed.

The goal of the procedure is to make a correct selection with high probability. The procedure follows the preference zone / indifference zone approach, wherein we require the selection procedure to guarantee a probability of at least 90% *correct* selection (of the truly best intervention), assuming that one is truly superior to the other by a pre-specified amount. This pre-specification defines a region in the parameter space called the *preference zone*. If the best intervention does not exceed the next best by the pre-specified amount, the success probabilities are said to lie in the *indifference zone*, where we shall be indifferent to the fact that the probability of correct selection may be less than 90%. For this trial, the preference zone consists of all parameter vectors (p_1, p_2) of success probabilities where the odds ratio comparing the largest to the next largest is greater than or equal to 2.15 ($p_1=0.35, p_2=0.20$).

The selection procedure is specified by the sampling rule, the stopping rule, and the terminal decision rule, as follows.

Sampling rule: Patients, when eligible, will be enrolled to the study at the “first-come-first-serve” basis. All the participating ICUs can have 2 possible “room type”: negative pressure rooms and non-negative pressure rooms. Each of the participating ICUs will be divided into either two or four clusters as follows. Any ICU with only one room type (i.e., it only has negative pressure rooms or only has non-negative pressure rooms) will be divided into 2 clusters. For ICUs that contain both room types (i.e., it has negative pressure rooms and non-negative pressure rooms), we will divide that ICU into 4 clusters with two clusters for each room type. Two clusters within each ICU and each room type will then be randomized to either of the study arms. Enrolled patients will receive

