the treatment according to the cluster of ICU they are assigned. Post-randomization pairing scheme will be employed to form the pairs if the stopping criterion is not reached at the time that first 60 outcomes have been observed. As the hospital administration changed the room type to accommodate the decrease of COVID patients (e.g., some negative pressure rooms were changed to non-negative pressure rooms), we currently recruitment included more patients in the prophylactic dose group than those of the intermediate dose group. Pending the approval of DSMB, in each ICU and each room type, we will randomize “intermediate dose rooms” and “prophylactic dose rooms” in a 3:1 ratio until we reach enrollment of 30 patients for one group and we will then only assign patients to the other group until we achieve the recruitment of 30 patients that group as well. After we recruit 30 patients for each arm, the ratio of the rooms will be changed back to 1:1 (intermediate vs. prophylactic) for the subsequent recruitment.

Success tallies:

Each time the follow-up for each patient in a pair is complete and a “good” or “poor” outcome is determined for each based on the composite primary outcome, the pair becomes “observed” and is available for sequential monitoring by adding to a running tally of the “good” outcomes for each intervention. These *success tallies* are used for the stopping rule.

Stopping and Decision rule: The criterion for stopping is a *difference of 4 or more between the tallies* if this occurs at or before 60 patients’ outcomes have been observed. At that time, intervention with the largest success tally is selected as the preferred intervention. However, we will not stop the procedure and make a decision before the outcomes of the first 60 patients have become available. In addition, if the criterion for stopping has not been reached at or before 100 outcomes have been observed, the trial will stop by *truncation* with a maximum of 100 patients. At that time, intervention with the largest success tally is selected as the preferred intervention. If there are ties for the largest success tally at time of truncation, we will select the intervention according to other considerations (safety, better secondary outcomes, etc.).

Incomplete pairs:

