To avoid bias in statistical inference due to bias in sampling, *only* the first 60 patients will be included in this set of analysis. Details explain why bias occurs and how it will affect the statistical inference can also be found in the supplemental appendix. We will use the data from these 60 patients to generate the proportions of patients with the events specified as primary and secondary outcomes. We will also report the descriptive statistics (mean, median, interquartile range) for the time to ICU discharge. Graphical display of the data will be done as well. To compare the intervention effect between the two study groups on the primary and secondary outcomes, we will use generalized linear model with identity link function for continuous variables and logit link function for dichotomous variables following the intent-to-treat principle. Covariates in these models include intervention group indicator, ICU indicators, and the potential confounding factors. The pre-specified potential confounders are age, sex, weight, estimated glomerular filtration rate (eGFR), concomitant treatment with an IL-6 inhibitor, and concomitant treatment with corticosteroids. Generalized estimating equations methodology will be employed to account for the within-ICU correlation for subject assignment to the same ICU area. The key parameter of interest is the regression coefficient corresponding to the intervention group indicator which is the mean difference for continuous outcomes and log-odds ratio for dichotomous outcomes and it represents intervention effect of intermediate-dose anticoagulation compared with that of prophylactic anticoagulation. To report the trial findings, we will present the mean difference and odds ratio when appropriate and their corresponding p-values and 95% confidence intervals. Several pre-specified sensitivity analyses will be conducted: (1) excluding the patients who undergo CRRT during the study period; (2) excluding patients who experienced deviation in anticoagulation from randomized treatment arm; (3) analyzing the patients as the treatment they actually received. Additional sensitivity analysis will also be conducted to include covariates found imbalanced between the two intervention groups.

Operating characteristics of the Study Design

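### The 60-patient logit/GEE model has too many parameters for about 16.5 expected successes, and its cluster and standard error are not specified

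*Combined protocol and SAP*

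**What the plan says.** The model is given in Section VIII, under the analysis for the first 60 patients, and repeated in the Design row of the Protocol Outline. It uses a logit link for binary endpoints and an identity link for continuous ones. On its terms: "Covariates in these models include intervention group indicator, ICU indicators, and the potential confounding factors". The six confounders are age, sex, weight, eGFR, "concomitant treatment with an IL-6 inhibitor, and concomitant treatment with corticosteroids". On correlation: "Generalized estimating equations methodology will be employed to account for the within-ICU correlation for subject assignment to the same ICU area". On reporting: "we will present the mean difference and odds ratio when appropriate and their corresponding p-values and 95% confidence intervals".

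The randomized unit is smaller than the ICU. General Design says "ICU subunits will be randomly assigned to give patients intermediate (higher) dose or prophylactic (lower) dose of anticoagulation", and the Sampling rule says "Two clusters within each ICU and each room type will then be randomized to either of the study arms", with two or four clusters per ICU. Membership is not fixed over time. The Sampling rule records that "some negative pressure rooms were changed to non-negative pressure rooms", and Study intervention says "Patients transferred between participating ICUs will remain in the treatment arm assigned at initial randomization".

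The documents do not give the number of ICUs, the GEE cluster variable, the working correlation, the variance estimator, a small-sample correction, or a rule for fits that separate. Minimizing Selection Bias defends estimation and testing in these 60 patients as free of bias.

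**The concern.** There are three difficulties.

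- **Model size.** Maximum-likelihood logistic estimates move away from the null when there are few events per parameter. A different standard error does not cure this, because the point estimate itself is off.
- **Sparse ICUs.** An ICU in which every patient fails (or every patient succeeds) has no finite coefficient, and its patients stop informing the arm comparison.
- **Variance.** One sentence names both the ICU and the ICU area. If the ICU is the cluster, the ICU indicators already absorb the ICU mean, so GEE adds little and correlation at the randomized level is left unaddressed. If the usual robust standard error is applied to so few clusters without correction, it is too small.

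At stake are the odds ratios, p-values and 95% intervals that the plan commits to report. The argument that these patients are unbiased concerns sampling only: recruitment of the first 30 pairs does not depend on outcomes. It does not cover bias from the fitted model.

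A smaller point is that the two concomitant treatments have no measurement time, so the model could adjust for care given after allocation.

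**Working it through.** **1. Check the design rates.** Scenario 1 of Table 1 uses 0.35 and 0.20. Simulating binomial tallies at 30 per arm, then pair by pair to a lead of 4 or 50 pairs (400,000 replications), gives expected total 68.4, expected failures 49.6, correct selection 95.2%, truncation 10.4% and stopping at 60 in 62.6%. The table has 68.4, 49.6, 95.1%, 10.2% and 62.6%. The rates are confirmed as the design inputs.

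**2. Expected successes in 60 patients.** 30 × 0.35 + 30 × 0.20 = 10.5 + 6.0 = 16.5. Scenario 3 (0.20 in both arms) gives 12.0.

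**3. Parameters.** Intercept 1 + arm 1 + ICU indicators (K − 1) + confounders 6 = K + 7.

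| K | Parameters | 16.5 / parameters | 12.0 / parameters |
|---|---|---|---|
| 2 | 9 | 1.83 | 1.33 |
| 3 | 10 | 1.65 | 1.20 |
| 4 | 11 | 1.50 | 1.09 |
| 6 | 13 | 1.27 | 0.92 |
| 8 | 15 | 1.10 | 0.80 |

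The unstated K does not rescue the model. This ratio matters for binary endpoints only. For continuous endpoints 60 − (K+7) residual degrees of freedom remain (45 at K = 8), and only the cluster and variance points apply.

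**4. Odds ratio.** Assumptions: 3/4/6/8 ICUs, two subunits per ICU, noise covariates, independence working correlation. With a true odds ratio of 2.15, the full model's median was 2.57/2.53/2.65/2.94 (600 trials per setting). A separate simulation with 2,000 trials per setting gave 2.59/2.62/2.76/3.00. Relative to the truth this runs from 2.53/2.15 = 1.18 to 3.00/2.15 = 1.40. A Firth penalty on the same full model gave medians of 2.05–2.13.

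**5. Sparse ICUs.** With equal ICU sizes and 27.5% success, the chance that at least one ICU has no success is 1 − (1 − 0.725^(60/K))^K = 0.5/3.2/21.8/52.8% at K = 3/4/6/8. Simulated fits with a non-finite coefficient or non-convergence were about 3/3/20/54%. At 3 ICUs most of these must have another cause, since the closed form gives only 0.5%. At 50% success the simulated figures fall to 0/0/1–3/8–15%.

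The arm estimate usually survives. At 0.20 vs 0.35 and equal ICU sizes, after leaving out ICUs with only failures or only successes, a finite arm odds ratio was lost in 1.5/1.7/2.4/2.8% of trials.

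**6. Rejection at a nominal 5% with no arm effect.**

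| Model | Standard error | Rejection |
|---|---|---|
| Full | Uncorrected robust, ICU clusters, ICC 0 | 11–27% |
| Full | Uncorrected robust, subunit clusters, ICC 0 | 16–33% |
| Full | Model-based, ICC 0 | about 6–9% |
| Full | Model-based, ICC 0.05 | about 9–13% |
| Full | Kauermann-Carroll, subunits, t on (subunits − 2) df | about 4–8% |
| Arm + one or two covariates | Kauermann-Carroll, subunits, same t | about 4–5% |

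A further simulation at 3/5/8 ICUs (27.5% in both arms, ICC 0) agrees closely: 25.3/15.3/9.3% by ICU, 31.4/23.5/18.4% by subunit, and 6.0/6.3/8.6% model-based. The smaller model's median odds ratio was 2.2–2.3.

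**The case against.** **This analysis decides nothing.** The Stopping and Decision rule selects by success tallies, and the full-sample section disclaims any declaration of significance. Raw proportions are also reported. This stands and limits the severity. One narrow exception is possible: a tie at truncation is settled on other considerations, which include secondary outcomes, and the plan does not say whether these would be modelled.

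**The worst error rates need a choice the plan never makes.** This is correct. A reader might infer that the plan's test rejects up to a third of the time. That holds only for an uncorrected robust standard error; with a model-based one the excess is modest.

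**A diverging ICU coefficient is not a failed analysis.** Also correct. The plan's stated target is the arm coefficient, which usually stays finite. The cost is lost information and a convergence warning, so the percentages in step 5 must not be read as the chance of losing the arm estimate.

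**The ICU indicators and confounders have a purpose.** Randomization is within ICU and room type. The 3:1 phase and then one-arm-only assignment could tie arm to calendar time. In an illustration with 4 ICUs, true odds ratio 1 and one omitted binary covariate (log-odds ratio 0.7, imbalance of 30 or 50 points, all assumed), the reduced model's median odds ratio was 1.21 or 1.45, against 1.00 or 1.10 for the full model. This stands: the documents do not support making a smaller model mandatory.

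**Corrections and ICU clusters.** A reader might infer that small-sample corrections are impossible with ICU clusters and ICU indicators. They are not: Kauermann-Carroll with a pseudo-inverse rejected 1.9–5.6%.

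None of this removes the inflation of the odds ratio, which does not depend on the standard error.

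**Conclusion.** The point holds as a cheap improvement to the analysis plan. The parameter count, the 16.5 expected successes, the ambiguous cluster and the missing variance estimator follow directly from the documents. That the model is too large is a judgment supported by simulation, not a contradiction of a stated figure.

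On the assumed settings the median odds ratio is about 2.5–3.0 at a true 2.15. The size of the p-value and interval problem depends on a standard error still to be chosen. The number of ICUs, subunits per ICU, intracluster correlation and covariate distributions are assumptions. The tally-based selection is not put in doubt. How length of stay handles death is a separate matter and forms no part of this point.

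**What to change.** Amend the 60-patient analysis section and the matching text in the Protocol Outline:

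- Name the GEE cluster as the randomized ICU subunit (ICU × room type × arm) recorded at enrolment, since rooms change type and patients move between ICUs. State the numbers of ICUs and subunits.
- Use a Kauermann-Carroll corrected robust standard error with t on (subunits − 2) degrees of freedom. Mancl-DeRouen is the more conservative choice.
- Estimate binary-endpoint odds ratios with a Firth-type penalty, which keeps the planned covariates. The combination of Firth estimates with the corrected robust standard error was not simulated and should be checked before use.
- Optionally add, as a sensitivity analysis, arm plus one or two enrolment-time covariates with the same corrected subunit standard error.
- Take IL-6 inhibitor and corticosteroid use as of enrolment wherever they are adjusted for.
- For components of the primary outcome with fewer than about 10 events, report counts by arm without a model.

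The cost is SAP wording, some programming and the simulation check. Intervals will be wider.

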The stopping criterion of a lead of at least 4 between largest and smallest success tallies was chosen to achieve a probability of correct selection of at least 90% for any true success probabilities lying in the preference zone characterized by an odds ratio of 2.15 or greater between the true success probabilities of the two interventions. For example, true success probabilities of 0.35 and 0.20 with an odds ratio of 2.15 is lying on the boundary between the preference and indifference zones. For any such configuration with $\{p_1/(1-p_1)\}/\{p_2/(1-p_2)\} = 2.15$, the selection procedure will result in a correct selection with at least 90% probability. Table 1 shows the operating characteristics of the selection procedure under various scenarios of true success probability configurations for the two arms.

TABLE 1
Operating characteristics of the selection procedure

Scenario 1. $p_1=0.35$, $p_2=0.20$, criterion for stopping is a difference of 4 between the tallies, truncation at 100 patients, minimum # of patients before possible selection=60						
ET	EF	PCS	P[truncation]	P[T=T ₀]	P[T=T ₀ ,CS]	P[CS T=T ₀]
68.4	49.6	95.1%	10.2%	62.6%	61.6%	98.4%
Scenario 2. $p_1=0.30$, $p_2=0.20$, criterion for stopping is a difference of 4 between the tallies, truncation at 100 patients, minimum # of patients before possible selection=60						
ET	EF	PCS	P[truncation]	P[T=T ₀]	P[T=T ₀ ,CS]	P[CS T=T ₀]
74.0	55.5.4	87.1%	21.5%	46.6%	44.0%	94.5%
Scenario 3. $p_1=0.20$, $p_2=0.20$, criterion for stopping is a difference of 4 between the tallies, truncation at 100 patients, minimum # of patients before possible selection=60						
ET	EF	PCS	P[truncation]	P[T=T ₀]	P[T=T ₀ ,CS]	P[CS T=T ₀]
83.0	66.4	50.2%	43.5%	25.7%	12.9%	50.2%

ET is the expected total number of patients

EF is the expected total number of patients with bad outcome

PCS is the probability of correct selection

P[truncation] is the probability that the trial will be truncated before reaching the criterion for stopping

P[T=T₀] is the probability of reaching a decision after exactly 60 patients (30 in each arm)

P[T=T₀, CS] is the probability of correct selection after exactly 60 patients (30 in each arm)

P[CS|T=T₀] is the conditional probability that correct selection is made given that exactly 60 patients (30 in each arm)

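### With truncation at 100 patients, the 90% correct-selection guarantee does not hold for every pair of success rates with an odds ratio of 2.15 or more; it fails at extreme rates, though not at the planned ones.

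*Combined protocol and SAP*

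**What the plan says.** Section VIII, Study Implementation, sets the goal: "we require the selection procedure to guarantee a probability of at least 90" per cent, provided one arm is truly better by a pre-specified amount. It defines that preference zone by the odds ratio alone: all pairs of success probabilities for which "the odds ratio comparing the largest to the next largest is greater than or equal to 2.15".

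Section VIII, Operating characteristics of the Study Design, says the lead of 4 was chosen to reach 90% "for any true success probabilities lying in the preference zone characterized by an odds ratio of 2.15 or greater". It then repeats, for every configuration with an odds ratio of exactly 2.15, that "the selection procedure will result in a correct selection with at least 90% probability". Neither place limits the success rates or makes an exception for truncation.

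The Stopping and Decision rule ends the trial by truncation "with a maximum of 100 patients" and selects the larger tally. Ties at that point are settled by other considerations, such as safety or secondary outcomes. Each scenario in Table 1 carries the same rule: "criterion for stopping is a difference of 4 between the tallies, truncation at 100 patients, minimum # of patients before possible selection=60". Only Scenario 1 lies on the boundary of the preference zone: "true success probabilities of 0.35 and 0.20 with an odds ratio of 2.15 is lying on the boundary". Its stated probability of correct selection is 95.1%.

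**The concern.** A bound that depends only on the odds ratio belongs to a lead-of-4 rule that runs until one arm is 4 ahead. Pairs with equal outcomes then only delay the decision. Once the number of pairs is capped, they also use up the sample. When both success rates are very low or very high, most pairs are equal, the cap usually binds first, and the choice rests on a lead of 1 to 3 or on a tie.

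The 90% figure is the stated goal of the design, and it is claimed for a whole region on the evidence of one boundary point. A reader who wants to know whether it survives an unexpected success rate finds no limit stated.

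**Working it through.** **Inputs, all from Section VIII.** Odds ratio 2.15; pairs allocated 1:1; no selection before 30 pairs (60 patients); a look after each later pair; stop at a lead of 4 or more; truncate at 50 pairs (100 patients) and select the larger tally. The Stopping and Decision rule words the criterion as applying at or before 60 patients. Following Study Implementation and Table 1, it is read here as applying from 60 up to 100. Assumptions: independent patients, and ties at truncation split evenly, with the extremes also shown.

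**Method.** Let D be the difference in success tallies, better arm minus worse. Its exact distribution at 30 pairs is that of the difference of two binomials. Each later pair moves D by +1 with probability p1(1−p2), by −1 with probability p2(1−p1), and otherwise not at all. Paths stop at D ≥ 4 or D ≤ −4. At 50 pairs, the remaining paths with D > 0 count as correct and D = 0 is a tie.

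**Reproducing Table 1, Scenario 1 (0.35 against 0.20).**

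| | Stated | Recomputed |
|---|---|---|
| Correct selection | 95.1% | 95.2% |
| Expected patients | 68.4 | 68.4 |
| Expected bad outcomes | 49.6 | 49.6 |
| Truncation | 10.2% | 10.4% |
| Decision at 60 patients | 62.6% | 62.6% |

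Scenario 2 gives 87.3% (stated 87.1%) and Scenario 3 gives 50.0% (stated 50.2%). The calculation therefore models the plan's own rule.

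**Without truncation.** The bound is OR⁴/(1+OR⁴). With 2.15⁴ = 21.37, this is 21.37/22.37 = 95.5%, whatever the rates. The exact untruncated value, with the 60-patient minimum, is 95.7% at a lower-arm rate of 0.05 and again at 0.90.

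**Why the cap matters.** The better-arm rate follows from p1/(1−p1) = 2.15 × p2/(1−p2).

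- At p2 = 0.05, p1 = 0.1017. A pair is discordant with probability 0.1017 × 0.95 + 0.05 × 0.8983 = 0.1415, about 50 × 0.1415 = 7.1 discordant pairs by the cap.
- At the design alternative the probability is 0.35 × 0.80 + 0.20 × 0.65 = 0.41, about 50 × 0.41 = 20.5 discordant pairs.

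**Along the 2.15 boundary, truncated at 100 patients.**

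| Lower rate p2 | p1 | Truncated | Correct, ties split | No tie credited | Every tie credited |
|---|---|---|---|---|---|
| 0.05 | 0.102 | 57.1% | 83.5% | 78.7% | 88.2% |
| 0.08 | 0.158 | 36.1% | 88.5% | 85.6% | 91.4% |
| 0.10 | 0.193 | 27.5% | 90.6% | 88.4% | 92.8% |
| 0.20 | 0.350 | 10.4% | 95.2% | 94.3% | 96.0% |
| 0.80 | 0.896 | 26.1% | 90.9% | 88.8% | 93.0% |
| 0.85 | 0.924 | 38.3% | 88.0% | 84.9% | 91.1% |
| 0.90 | 0.951 | 57.9% | 83.3% | 78.5% | 88.1% |

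At p2 = 0.05 the 83.5% is made up of 41.2% correct by a lead of 4, 37.6% ahead at truncation, and half of a 9.5% tie probability. A simulation with 200,000 replications also gives 83.5% at 0.05 and 83.3% at 0.90.

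**Where 90% is met.** Solving for 90% gives lower-arm rates of 0.094 to 0.818 with ties split and 0.116 to 0.780 with no tie credited. Rounded inward, the second range is about 0.12 to 0.77. With every tie credited the range is 0.065 to 0.871.

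**Sensitivity.**

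- The Estimated Sample Size row of the protocol outline gives a maximum of 150. With truncation there and ties split, the values are 88.3% at 0.05 and 88.2% at 0.90. They pass 90% (91.2% and 91.1%) only if every tie is credited.
- At an odds ratio of 2.5 and truncation at 100, the values are 88.6% and 86.9% with ties split, and 92.2% and 91.1% with every tie credited.

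**The case against.** The failing rates are far from anything the plan expects. The design alternative is 0.35 against 0.20, and the worked tallies in the likelihood-ratio section have lower-arm rates of 6/30 to 10/30, all well inside the safe range. At a lower-arm rate of 0.05 or 0.90, an odds ratio of 2.15 is a difference of only about 5 percentage points; the plan calls the 15-point design alternative minimally meaningful. Truncation is disclosed, and Scenario 1's 95.1% already includes it. A blinded interim look at the combined event rate is planned, and it would show rates near these extremes.

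All of this limits the importance of the point, and it stands to that extent. It does not make the universal statement true: the preference zone is defined by odds ratio alone, and the 90% is claimed for all of it.

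A reader might also infer that a trial with extreme rates would be reported as carrying the 90% guarantee. The documents do not say so. The result is to be reported as a likelihood ratio at the observed proportions. After truncation the exponent is the actual tally difference, so a narrow lead would show as weak evidence.

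Nor is the 87.1% in Scenario 2 a counterexample. Its odds ratio is (0.30/0.70)/(0.20/0.80) = 1.71, which is in the indifference zone.

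**Conclusion.** The statement is wrong as written. On the 2.15 boundary, correct selection is about 83.5% at a lower-arm rate of 0.05 and 83.3% at 0.90. At these two rates it stays below 90% however ties are treated: about 88% at best and 78-79% at worst. Nearer the edges, for example at 0.08 or 0.85, the tie convention decides whether 90% is met.

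A reader might infer that the design is underpowered for its purpose or that Table 1 is miscalculated. Neither follows: correct selection is about 95% at the planned rates, and the Table 1 figures checked agree to within simulation error. The defect is an overstated guarantee.

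The result assumes independent patients, so it does not depend on clustering. It also assumes 1:1 pairs, the reading of the stopping rule given above, and truncation at 100.

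**What to change.** In Study Implementation and in Operating characteristics of the Study Design, replace the universal claim with wording such as: *at least 90% on the odds-ratio 2.15 boundary when the lower success probability is between about 0.12 and 0.77, given truncation at 100 patients and not counting ties at truncation as correct (about 0.10 to 0.80 if ties are split evenly).* The tie condition is needed because the plan does not settle ties by chance: with no tie credited, a bare range of 0.10 to 0.80 would fail at its ends (88.4% and 88.8%).

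Add boundary rows to Table 1, for example at lower-arm rates of 0.05 and 0.90, and state the tie convention used in the simulation.

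The cost is a few sentences and two more simulated rows. The stated guarantee becomes narrower. Conduct, sample size and stopping rule do not change.
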